12.1.3. Severity Criteria

The severity assessment for an adverse event or serious adverse event should be completed using the NCI-CTCAE Version 4.03. Any adverse event or serious adverse event not listed in the NCI-CTCAE Version 4.03 will be graded according to investigator clinical judgment by using the standard grades as follows:

Grade 1 (Mild): Awareness of symptoms that are easily tolerated, causing minimal discomfort and not interfering with everyday activities

Grade 2 (Moderate): Sufficient discomfort is present to cause interference with normal activity

Grade 3 (Severe): Extreme distress, causing significant impairment of functioning or incapacitation. Prevents normal everyday activities

Grade 4: Life-threatening or disabling adverse event

Grade 5: Death related to the adverse event

The investigator should use clinical judgment in assessing the severity of events not directly experienced by the subject (eg, laboratory abnormalities).

12.2. Special Reporting Situations

Safety events of interest on a Sponsor study drug that may require expedited reporting or safety evaluation include, but are not limited to:

- Overdose of a Sponsor study drug
- Suspected abuse/misuse of a Sponsor study drug
- Accidental or occupational exposure to a Sponsor study drug
- Medication error involving a Sponsor product (with or without subject/patient exposure to the Sponsor study drug, eg, name confusion)
- Exposure to a Sponsor study drug from breastfeeding

Special reporting situations should be recorded in the CRF. Any special reporting situation that meets the criteria of a serious adverse event should be recorded on the serious adverse event page of the CRF.

12.3. Procedures

12.3.1. All Adverse Events

All adverse events and special reporting situations will be reported from the time a signed and dated ICF is obtained until 30 days after the last dose of study drug (or 90 days for serious adverse events), or until start of subsequent anticancer therapy or the subject withdraws consent

for study participation, if earlier, which may include contact for follow-up of safety. For subjects who have received subsequent treatment with therapeutic intent for NSCLC during the adverse event reporting period, only adverse events that are considered to be possibly, probably, or definitely related to atezolizumab or daratumumab need to be reported. Serious adverse events, including those spontaneously reported to the investigator, must be reported using the Serious Adverse Event Form. The Sponsor will evaluate any safety information that is spontaneously reported by an investigator beyond the time frame specified in the protocol.

Disease progression should not be recorded as an adverse event or serious adverse event term; instead, signs and symptoms of clinical sequelae resulting from disease progression/lack of efficacy will be reported if they fulfill the serious adverse event definition (refer to Section 12.1.1). Death should not be recorded as an adverse event or serious adverse event, but as the outcome of an adverse event. The adverse event that resulted in the death should be reported as a serious adverse event. All events that meet the definition of a serious adverse event will be reported as serious adverse events, regardless of whether they are protocol-specific assessments. Anticipated events will be recorded and reported as described in [Attachment 4](#).

All adverse events, regardless of seriousness, severity, or presumed relationship to study drug, must be recorded using medical terminology in the source document and the CRF. Whenever possible, diagnoses should be given when signs and symptoms are due to a common etiology (eg, cough, runny nose, sneezing, sore throat, and head congestion should be reported as "upper respiratory infection"). Investigators must record in the CRF their opinion concerning the relationship of the adverse event to study therapy. All measures required for adverse event management must be recorded in the source document and reported according to Sponsor instructions.

The Sponsor assumes responsibility for appropriate reporting of adverse events to the regulatory authorities. The Sponsor will also report to the investigator (and the head of the investigational institute where required) all suspected unexpected serious adverse reactions (SUSARs). For anticipated events reported as individual serious adverse events the Sponsor will make a determination of relatedness in addition to and independent of the investigator's assessment. The Sponsor will periodically evaluate the accumulating data and, when there is sufficient evidence and the Sponsor has determined there is a reasonable possibility that the drug caused a serious anticipated event, they will submit a safety report in narrative format to the investigators (and the head of the institute).

The investigator (or Sponsor where required) must report SUSARs to the appropriate Independent Ethics Committee/Institutional Review Board (IEC/IRB) that approved the protocol unless otherwise required and documented by the IEC/IRB.

Subjects (or their designees, if appropriate) will be provided with a "wallet (study) card" and instructed to carry this card with them for the duration of the study indicating the following:

- Study number
- Statement, in the local language(s), that the subject is participating in a clinical study
- Investigator's name and 24-hour contact telephone number
- Local Sponsor's name and 24-hour contact telephone number (for medical staff only)
- Site number
- Subject number
- Blood type and IAT (as described in Section 9.7).

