Adverse events ^b		Continuous from ICF through 30 days (or 90 days for SAEs) after the last dose of study drug or start of subsequent anticancer therapy, if earlier (see Section 12.3.1)									
Prior and Concomitant Medications		Continuous 30 days prior to 1st administration of study drug through 30 days after last dose of study drug									
Survival and subsequent anti-cancer therapy											X

AE=adverse event, C=cycle, CRF=case report form, COPD=chronic obstructive pulmonary disease, CT=computed tomography, D or d=day, ECOG= Eastern Cooperative Oncology Group Performance Status, EOT=end of treatment, FEV-1=forced expiratory volume; maximal amount of air forcefully exhaled in 1 sec., HBV=hepatitis B virus, HCV=hepatitis C virus, IAT=indirect antiglobulin test, ICF=informed consent form, MRI=magnetic resonance imaging, PD=progressive disease, PD-L1=programmed death-ligand 1, Ph=phase, q=every, SIPPM=Site Investigational Product Procedures Manual

- Safety Run-in and Arm B only:** C1D1: measure vital signs immediately before the start of the infusion; at 0.5, 1, 1.5, 2 and 3.5 hrs after the start of the infusion; at the end of the infusion; and 0.5 and 1 hr after the end of the infusion. For all subsequent Safety Run-in and Arm B administrations (daratumumab + atezolizumab), measure immediately before the administration start, at the end of the atezolizumab infusion, and as clinically indicated. **Arm A only:** vital signs should be assessed at Screening, within 24 hrs of the start of each infusion and at the end of each infusion.
- Beginning with the implementation of Amendment 7, only serious adverse events will be reported and entered in the Sponsor safety repository for subjects who continue to be treated according to local regulatory approval and standard of care guidelines.^{50,51}

ABBREVIATIONS

ADCC	antibody dependent cell-mediated cytotoxicity
AE	adverse event
ALK	anaplastic lymphoma kinase
Breg	regulatory B cell
CBC	complete blood count
CBR	clinical benefit rate
CDC	complement-dependent cytotoxicity
COPD	chronic obstructive pulmonary disease
CR, sCR	complete response; stringent complete response
CRF	case report form(s) (paper or electronic as appropriate for this study)
CT	computed tomography
CyTOF	cytometry time of flight
DCF	data clarification form
DLT	dose-limiting toxicity
DMC	Data Monitoring Committee
DoR	duration of response
ECG	electrocardiogram
ECOG	Eastern Cooperative Oncology Group Performance Status

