12.4. Safety Reporting for Atezolizumab Monotherapy Subjects (per Amendment 6)

Following implementation of Amendment 6, all adverse events and special reporting situations (with the exception of Grade 1 to 2 events and non-immune-mediated events) will be reported from the time a signed and dated ICF is obtained until 30 days after the last dose of study drug (or 90 days for serious adverse events), or until withdrawal of consent for study participation. For subjects who have received subsequent treatment with therapeutic intent for NSCLC during the adverse event reporting period, only adverse events that are considered to be possibly, probably, or definitely related to atezolizumab need to be reported; all other Grade 1 to 2 AEs, including laboratory abnormalities, do not need to be recorded in the CRF, but should be recorded in the source documentation.

Beyond 90 days after the last dose of study drug, SAEs, considered possibly, probably, or definitely related to study drug will continue to be collected and reported into the Sponsor's global safety database, using the SAE Form (paper form) faxed to Sponsor's Local Operational Company/Local Safety Officer. These should be reported until the subject discontinues the study (per the definitions in Section 10.2). SAEs (see Section 12.3.2) should include information on study agent administration and concomitant medications and other treatments associated with the SAE.

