2.6.10. Treatment Emergent Adverse Events

Treatment emergent adverse events (TEAEs) are defined as any AE with onset date and time on or after that of the first dose through 30 days after the last study drug administration, or the day prior to start of subsequent therapy, whichever is earlier; or any AE that is considered related to (very likely, probably, or possibly related) study medication regardless of the start date of the event. AEs with missing or partial onset date and time will be considered as treatment-emergent unless the onset date and time of an AE can be determined as earlier than that of the first dose, or later than 30 days after last study drug administration.

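### Protocol 12.3.1 and Table 1 stop adverse event reporting at new anticancer therapy, yet the next sentence of 12.3.1 and SAP 2.6.10 rely on related events after it, so these may be under-counted in both arms

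*Protocol*

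**What the plan says.** Five places bear on what a site reports once a subject starts another anticancer treatment.

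- **Protocol 12.3.1, opening sentence.** Reporting runs from consent to 30 days after the last dose ("or 90 days for serious adverse events), or until start of subsequent anticancer therapy or the subject withdraws consent", if either comes earlier.
- **Protocol 12.3.1, next sentence.** "For subjects who have received subsequent treatment with therapeutic intent for NSCLC during the adverse event reporting period", the protocol says, "only adverse events that are considered to be possibly, probably, or definitely related to atezolizumab or daratumumab need to be reported".
- **Protocol Table 1, adverse events row.** Collection is continuous to 30 days (90 for serious events) "after the last dose of study drug or start of subsequent anticancer therapy, if earlier (see Section 12.3.1"). The row states the stop and no exception for related events, but it does point to 12.3.1.
- **Protocol 12.3.2.** Every serious event occurring during the study goes to the sponsor within 24 hours. The section gives no end date and does not mention new therapy.
- **SAP 2.6.10.** An event is treatment-emergent if it starts between the first dose and 30 days after the last dose, or the day before subsequent therapy if that is sooner, "or any AE that is considered related to (very likely, probably, or possibly related) study medication regardless of the start date of the event".

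Protocol 12.4, added by Amendment 6 for subjects continuing on atezolizumab alone, runs "until 30 days after the last dose of study drug (or 90 days for serious adverse events), or until withdrawal of consent". It has no stop at new therapy. After new therapy it keeps related events only.

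**The concern.** Under the opening sentence of 12.3.1, the reporting period is over once new therapy starts. The next sentence then sets a duty for subjects who received new therapy within that period. Taken literally, it has nothing left to act on.

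The analysis depends on the answer. SAP 6.1 summarises only treatment-emergent events unless stated otherwise. After new therapy, an event can enter those tables only through the related-event part of the definition in SAP 2.6.10. A site that follows the stop in Table 1 would not send the events that this part is meant to count.

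The interval after the last dose matters for these drugs. Protocol 6.2.1 warns that stopping atezolizumab may not bring immune-mediated toxicity under control at once. What is at stake is the completeness and consistency of late related toxicity, in a trial with safety of the combination as a secondary objective.

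**Working it through.** The documents give no figure to reproduce. The check compares the rules for one subject. Let L be the last dose, N the start of new therapy, and t = N − L in days, with N before the window closes and consent not withdrawn.

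| Source | Related non-serious event after N | Related serious event after N |
|---|---|---|
| 12.3.1, opening sentence | not reported | not reported |
| 12.3.1, next sentence | reported, end date unclear | reported, end date unclear |
| Table 1 row, as worded | not reported | not reported |
| 12.3.2 | not addressed | reported, no end date |
| SAP 2.6.10 | counted if collected | counted if collected |

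**Step 1, literal reading.** The opening sentence ends the period at the earliest of L + 30 (L + 90 for serious events), N, and withdrawal of consent. If N comes first, the period ends at N, and the related-event sentence covers no time after it.

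**Step 2, reconciling reading.** The general duty ends at N, but related events continue to L + 30 or L + 90. This gives the second sentence a purpose and fits the two-part definition in SAP 2.6.10. No passage states it.

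**Step 3, serious events.** If 12.3.2 has no time limit, the 90-day limit in 12.3.1 serves no purpose. If 12.3.2 is bounded by 12.3.1, the stop at new therapy applies to serious events too. Section 12.3.2 therefore has to be reconciled along with the others.

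**Step 4, length of the interval in doubt.** It is 30 − t days for non-serious events (zero once t reaches 30) and 90 − t days for serious events. The values of t below are assumptions, because the documents give no timing.

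| t (days) | Non-serious | Serious |
|---|---|---|
| 15 | 30 − 15 = 15 days (15/30 = 50%) | 90 − 15 = 75 days (75/90 = 83%) |
| 30 | 0 | 90 − 30 = 60 days (60/90 = 67%) |
| 60 | 0 | 90 − 60 = 30 days (30/90 = 33%) |

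These are shares of one subject's window, not shares of events lost. For serious events they apply only where a site follows the stop rather than 12.3.2.

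**Step 5, which data are affected.** Protocol 3.2 and 17.9.1 base the clinical study report on the data reviewed on 23 May 2018. Amendment 6, which brought in 12.4, is dated 14 August 2018. Those data were therefore collected before 12.4 existed.

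**Step 6, attribution terms.** Sections 12.3.1 and 12.4 refer to events definitely related. The scale in Protocol 12.1.2, and the rule in SAP 2.6.9, use possible, probable and very likely, with no category called definite.

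**The case against.** The best defence is that sites would read 12.3.1 sensibly: report everything until new therapy, then related events to day 30 or 90. Table 1 sends them to that section, and SAP 2.6.10 has the same shape, with a general cut at new therapy and an exception for related events. This reading is plausible, and it is probably what was meant. It is not written down, and the schedule row gives only the stop.

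There are also safeguards. Section 12.3.2 covers serious events. The sponsor evaluates late reports that arrive spontaneously. Section 12.4 has no stop at new therapy. Each is partial: 12.3.2 does not fit with the 90-day limit, evaluating spontaneous reports does not oblige sites to send them, and 12.4 came after the data used for the report. Protocol 9.1.4 asks that the End-of-Treatment visit, due 30 days after the last dose, take place before the next treatment where possible. Where that happens, little or none of the non-serious window is in doubt.

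It is fair to add that rewording cannot now recover events that were never sent. Protocol 17.5 ends electronic data capture with Amendment 7.

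A reader might infer three stronger things that the documents do not support.

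- **That the loss falls mainly on Arm B.** Only Arm A subjects could cross over at progression and stay on study drug, so Arm B subjects might reach outside therapy sooner. However, the rule is the same in both arms, and no by-arm timing of new therapy or crossover uptake is given. Crossover only postpones outside therapy, and Arm B subjects could also be treated beyond progression with approval (9.4.2).
- **That it bears on the excess of deaths in the combination arm.** Date and cause of death come from survival follow-up (9.1.5), and SAP 6.2 summarises all deaths during the study. Death counts do not depend on the adverse event window. Protocol 1.4 also reports no unexpected imbalance in on-treatment toxicity.
- **That 12.4 already requires all serious events after new therapy.** It keeps only related events at that point.

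**Conclusion.** The inconsistency is real. The opening sentence of 12.3.1 and Table 1 stop all reporting at new therapy. The next sentence of 12.3.1 asks for related events after it, 12.3.2 asks for all serious events, and SAP 2.6.10 would count related events if they arrived. Related events from new therapy to day 30, and related serious events to day 90, may therefore have been collected inconsistently and under-counted in both arms.

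The interval per affected subject is the one in the working. The number of subjects affected and the number of events missed cannot be worked out from the documents. The conclusion assumes only that some subjects start new therapy inside a window and that some sites follow the stop as written. An uneven loss by arm is possible, but the documents do not show it. Counting by arm would settle the matter.

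**What to change.** Write one rule and use it in 12.3.1, Table 1 and 12.3.2. The stop at new therapy applies to unrelated events only. Events judged possibly, probably or very likely related on the 12.1.2 scale are reported to day 30, or day 90 if serious, whether or not new therapy has started. Replace the word definitely in 12.3.1 and 12.4 with the category in the scale. This agrees with the related-event sentences in 12.3.1 and 12.4 and with SAP 2.6.10, which needs no change.

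For data already collected, the remedy is disclosure. The clinical study report should state which rule sites applied and, by arm, how many subjects started new therapy within 30 days and within 90 days of the last dose. Subsequent anticancer treatment is collected under Protocol 9.1.5 and summarised under SAP 4.7, so the counts need no new data item.

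The cost is a sentence in 12.3.1, matching wording in Table 1 and 12.3.2, one short table in the report, and a small amount of extra site reporting where the rule still applies.

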12.3.2. Serious Adverse Events

All serious adverse events occurring during the study must be reported to the appropriate Sponsor contact person by study-site personnel within 24 hours of their knowledge of the event.

Information regarding serious adverse events will be transmitted to the Sponsor using the Serious Adverse Event Form, which must be completed and signed by a physician from the study site, and transmitted to the Sponsor within 24 hours. The initial and follow-up reports of a serious adverse event should be made by facsimile (fax).

All serious adverse events that have not resolved by the end of the study, or that have not resolved upon discontinuation of the subject's participation in the study, must be followed until any of the following occurs:

- The event resolves
- The event stabilizes
- The event returns to baseline, if a baseline value/status is available
- The event can be attributed to agents other than the study drug or to factors unrelated to study conduct
- It becomes unlikely that any additional information can be obtained (subject or health care practitioner refusal to provide additional information, lost to follow-up after demonstration of due diligence with follow-up efforts)

Suspected transmission of an infectious agent by a medicinal product will be reported as a serious adverse event. Any event requiring hospitalization (or prolongation of hospitalization) that occurs during the course of a subject's participation in a study must be reported as a serious adverse event, except hospitalizations for the following:

- If the subject has not experienced a significant medical event but is hospitalized overnight only for observation following infusion of atezolizumab or daratumumab, then the hospitalization should not be reported as a serious adverse event
- Hospitalizations not intended to treat an acute illness or adverse event (eg, social reasons such as pending placement in long-term care facility)
- Surgery or procedure planned before entry into the study (must be documented in the CRF). Note: Hospitalizations that were planned before the signing of the ICF, and where the underlying condition for which the hospitalization was planned has not worsened, will not be considered serious adverse events. Any adverse event that results in a prolongation of the originally planned hospitalization is to be reported as a new serious adverse event.

12.4. Safety Reporting for Atezolizumab Monotherapy Subjects (per Amendment 6)

Following implementation of Amendment 6, all adverse events and special reporting situations (with the exception of Grade 1 to 2 events and non-immune-mediated events) will be reported from the time a signed and dated ICF is obtained until 30 days after the last dose of study drug (or 90 days for serious adverse events), or until withdrawal of consent for study participation. For subjects who have received subsequent treatment with therapeutic intent for NSCLC during the adverse event reporting period, only adverse events that are considered to be possibly, probably, or definitely related to atezolizumab need to be reported; all other Grade 1 to 2 AEs, including laboratory abnormalities, do not need to be recorded in the CRF, but should be recorded in the source documentation.

Beyond 90 days after the last dose of study drug, SAEs, considered possibly, probably, or definitely related to study drug will continue to be collected and reported into the Sponsor's global safety database, using the SAE Form (paper form) faxed to Sponsor's Local Operational Company/Local Safety Officer. These should be reported until the subject discontinues the study (per the definitions in Section 10.2). SAEs (see Section 12.3.2) should include information on study agent administration and concomitant medications and other treatments associated with the SAE.

12.5. Safety Reporting for Atezolizumab Monotherapy Subjects (per Amendment 7)

Beginning with the implementation of Amendment 7, data from safety evaluations performed according to local regulatory approvals and standard of care guidelines^{50,51} will no longer be collected with the exception of serious adverse events that are to be reported and entered in the Sponsor safety repository.

12.6. Pregnancy

All initial reports of pregnancy in female subjects or partners of male subjects must be reported to the Sponsor by the study-site personnel within 24 hours of their knowledge of the event using the appropriate pregnancy notification form. Abnormal pregnancy outcomes (eg, spontaneous abortion, fetal death, stillbirth, congenital anomalies, ectopic pregnancy) are considered serious adverse events and must be reported using the Serious Adverse Event Form. Any subject who becomes pregnant during the study must be promptly withdrawn from the study and discontinue further study treatment.

Because the effect of the study drug on sperm is unknown, pregnancies in partners of male subjects included in the study will be reported as noted above.

Follow-up information regarding the outcome of the pregnancy and any postnatal sequelae in the infant will be required.

